3. PATIENT SELECTION

3.1 Eligibility Criteria

3.1.1 Newly diagnosed and pathologically-confirmed AML, confirmed by a bone marrow aspirate and/or biopsy and/or peripheral blood with $\geq 20\%$ myeloid blasts. Bone marrow biopsy, or aspirate or peripheral blood that were obtained up to 3 weeks before signing consent are allowed for purposes of confirming AML diagnosis for eligibility purposes. Secondary AML that is arising from prior myelodysplastic syndrome [MDS] as well as t-AML) are also allowed. Clarifications: . AML arising from myeloproliferative neoplasms (MPN), MPN/MDS overlap (including chronic myelomonocytic leukemia [CMML]) or another myeloid malignancy are NOT allowed. Note 1: Patients must have evidence of bone marrow involvement on aspirate or biopsy. Patients with only extramedullary disease and no bone marrow involvement will be excluded. Note 2 : Every effort should be made to get an aspirate for central flow assessment at screening and all subsequent required time points, but in cases where an aspirate cannot be collected-including dry taps-the patient will not be excluded and assessments will be performed on PB which should be collected at every time that BM is collected. Note 3: Some patients with AML require initiation of therapy quickly after diagnosis, and full metaphase karyotype results in some centers can take 2-3 weeks to result. To avoid this issue being an impediment to accrual to study or to cause delays in initiation of therapy in patients who need fast initiation of therapy, we allow use of karyotype and/or FISH results (as well as FLT3 results) on samples from blood or marrow that were obtained up to 3 weeks before signing consent for purposes of eligibility and stratification. In any case, results from FISH or karyotype should show if CBF abnormalities are present by time of randomization as the presence of CBF abnormalities is a required stratification factor.

3.1.2. Age ≥ 18 and ≤ 75 years.

Because no dosing or AE data are currently available on the use of Pembrolizumab (MK-3475) in patients < 18 years of age, children are excluded from this study, but will be eligible for future pediatric trials.

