7.1.2 Consolidation therapy phase

Consolidation therapy will consist of up to four cycles of infusional HiDAC and Pembrolizumab (MK-3475) (intervention arm) vs. HiDAC alone (control arm). Patients <60 years of age will receive 3 g/m² every 10-12 hours (Q12H) on Days 1, 3, and 5 (total 6 doses). Patients ≥60 years of age will receive 1.5 g/m² Q12H on Days 1, 3, and 5 (total 6 doses). Cycle 1 of consolidation therapy must start within 4 weeks of documenting remission status. Each cycle lasts ~28 days (up to 42 days). Patients in the intervention arm will continue to receive MK-3475 (pembrolizumab) Q3W (±3 days). Do not administer pembrolizumab concurrently with HiDAC chemotherapy Days 1-5 of each consolidation cycle. For consideration of timing of pembrolizumab, allow at least 3 hours after completion of chemotherapy prior to pembrolizumab

administration. Administration window for pembrolizumab may be extended to allow for this timing as necessary. After Cycle 1 of HiDAC, bone marrow assessment will be performed at the time of count recovery (same rules apply as post induction bone marrow in case of lack of count recovery) for formal assessment of response and MRD. Patients, who remain in CR or CRi, will be allowed to proceed to up to 3 more cycles of HiDAC and Pembrolizumab (MK-3475) (intervention arm) vs. HiDAC alone (control arm). Patients, who are not in CR or CRi will be taken off study. . If Pembrolizumab (MK-3475) is discontinued for any reason (after at least one dose of Pembrolizumab), the patient should continue Consolidation therapy on study.

Consolidation Therapy Regimen Description					
Agent	Premedications ; Precautions	Dose*	Route	Schedule	Cycle Length
Pembrolizumab (MK-3475) (For Intervention Arm only)	Premedication with antipyretic and antihistamine may be considered. No premedication with steroids	200 mg See Section 8.1 for instructions on the preparation of the infusion solution.	IV over 30 minutes (between 25-40 minutes) using an infusion set containing a low-protein binding 0.2 to 5 µm in-line filter. See Section 8.1 for compatible infusion set materials including in-line filter.	Q3W (±3 days) continuous from Day 8 of Induction. For consideration of timing of pembrolizumab, allow at least 3 hours after completion of chemotherapy prior to pembrolizumab administration	28 days (±7 days)

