The Kaplan-Meier method and log-rank test will be used to estimate the distribution of survival between/among different marker strata. Univariate or Multivariate cox proportional hazard models will be employed to explore the significance of biomarkers on survival outcomes, while adjusting for the potential prognostic factors. The interaction effects between treatment and biomarkers also will be evaluated. Serial measurements of biomarkers will be estimated at baseline, end of induction, post-consolidation cycle 1 and 4, every 3 months during maintenance, one year, and end of treatment when applicable. Landmark analysis (Benjamini *et al.*, 1995, Dafni *et al.*, 2011) or joint modeling (Huang *et al.*, 2016) will be used to assess serial measurements of biomarkers dynamical impacts on survival outcomes, where appropriate.

Part 3: Compare the biomarkers effects between treatment arms, intensive chemo + pembro vs. intensive chemo only.

The associations between treatment arms and baseline biomarkers will be evaluated using Chi-squared test/ Fisher's exact test, ANOVA, and the Mann-Whitney U tests as appropriate. Trajectory trends of the changes in markers' values or status across the measurement time will be explored using generalized linear mixed models. The bar plots and trajectory time plots will visually show the differences over time between treatment arms. The associations between markers and the demographic/prognostic factors will also be assessed using the similar statistical methods.

Part 4: Evaluate the correlations between biomarkers.

The correlations between biomarkers will be evaluated using Pearson/Spearman rank-order correlation coefficients, Chi-squared/Fisher's exact tests, and Wilcoxon rank sum / Kruskal-Wallis tests as appropriate. A scatter plot, boxplot, and mosaic plot will also be generated for visualization. The multiplicity of the endpoints will be adjusted using the correction of Benjamini and Hochberg (Benjamini *et al.*, 1995).

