Bone marrow biopsy	X										X ⁿ				X				X ^o		X	X		X ^s				
Stool	X														X ^z													
Research Blood Draws	X									X ^m	X ⁿ				X				X ^o	X ^q	X ^r	X ^r		X ^s				
Skin Punch Biopsy ^α	X																											
Transthoracic ECHO (TTE) or MUGA	X								X ^t																			
CT chest	X ^s																											

- a If the patient does not have a CR/CRi before starting this part of the study, the patient should go off study. Patients <65 may complete 3-4 cycles of consolidation therapy. Patients ≥65 years old may complete 1-2 cycles of consolidation therapy.
- b End of treatment visit will be immediately following final dose of Pembrolizumab (MK-3475).
- c After completing study treatment, clinical follow-up assessments are required every 6 months from date of therapy discontinuation. Common clinical practice should be monitored by institutional practice (*i.e.*, every 3 months though not required by protocol), but assessment results are only required every 6 months (+/- 14 days). All participants should be followed for survival to 3 years after end of treatment. For patients who achieve undetectable MRD during study treatment, central MRD assessments should continue in addition to general clinical follow.
- d Cytarabine should be dosed as appropriate for each phase of the study. Daunorubicin (60 mg/m²/day) or Idarubicin (12 mg/m²/day)
- e If patient has residual leukemia at the time of bone marrow aspiration, the patient may receive a 5+2 administration of these drugs. Adjust anthracycline dose as per institutional standards for Re- Induction.
- f Only for patients randomized to Arm B at 200 mg. Pembrolizumab (MK-3475) will be administered on Day 8 of induction and then Q3 weeks (+/- 3 days). Do not administer pembrolizumab concurrently with HIDAC chemotherapy Days 1-5 of each consolidation cycle. For consideration of timing of pembrolizumab, allow at least 3 hours after completion of chemotherapy prior to pembrolizumab administration. Administration window for pembrolizumab may be extended to allow for this timing as necessary. Each cycle of Maintenance is 21 days with pembrolizumab given on day 1 of each cycle up to 2 years.
- g Note: Performance status evaluations are based on a 4-week cycle. At minimum, performance status should be evaluated at the beginning of every cycle.

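### Section 7.1.2 allows up to four consolidation cycles with no age limit, while the study calendar allows one or two from age 65; the two rules must be reconciled

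*Combined protocol and SAP*

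**What the plan says.** Section 7.1.2 sets a ceiling for the intervention arm, "Consolidation therapy will consist of up to four cycles of infusional HiDAC and Pembrolizumab (MK-3475"), with high-dose cytarabine alone in the control arm. After the marrow that follows cycle 1, patients still in CR/CRi "will be allowed to proceed to up to 3 more cycles of HiDAC and Pembrolizumab (MK-3475"), again with a chemotherapy-only counterpart. Remission status is the only stated condition for going on. Age enters only through the dose: "Patients ≥60 years of age will receive 1.5 g/m² Q12H on Days 1, 3, and 5 (total 6 doses"). On duration the section says "Each cycle lasts ~28 days (up to 42 days").

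In Section 12, footnote a is attached to the consolidation heading and to the column for cycles 2 to 4. It reads "Patients <65 may complete 3-4 cycles of consolidation therapy", and then "Patients ≥65 years old may complete 1-2 cycles of consolidation therapy".

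Four other places bear on this:
- Eligibility (Section 3.1) is "Age ≥ 18 and ≤ 75 years", so the older group is enrolled, and Section 10.3 stratifies randomization at 65.
- Section 7.1.3 takes the end-of-consolidation marrow after whichever cycle is last, and counts the two-year maintenance limit from the first day of maintenance.
- MRD-negative CR after the last consolidation cycle is a secondary objective and endpoint (Sections 1.2.3 and 10.4.1.1).
- The biomarker plan (Section 10.4.2.8, Part 2) says "Serial measurements of biomarkers will be estimated at baseline, end of induction, post-consolidation cycle 1 and 4".

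**The concern.** Two current sections give different rules for how much chemotherapy an older patient may receive, and neither refers to the other. The calendar is what sites schedule from; Section 7.1.2 is what they treat from. For a patient aged 65 or over who is in remission after cycle 2, one section permits a third cycle and the other, on its natural reading, does not. A monitor could not say whether that cycle follows the protocol or deviates from it.

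At stake are the permitted exposure in one randomization stratum, the date of the marrow for a named secondary endpoint, the mandatory end-of-consolidation specimens (Section 5.1) and the start of maintenance. Pembrolizumab continues every three weeks through consolidation, and the two-year maintenance limit starts only afterwards. In the intervention arm the cycle rule therefore also changes total time on pembrolizumab.

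**Working it through.** **The plan's own figure first.** Section 10.1 gives about 71% power for 75% against 50%, 25 per arm, one-sided alpha 0.1. With the pooled Z-test:
- Mean rate = (0.50 + 0.75)/2 = 0.625.
- Null SE = sqrt(2 × 0.625 × 0.375/25) = 0.1369.
- Alternative SE = sqrt((0.50 × 0.50 + 0.75 × 0.25)/25) = 0.1323.
- Power = Φ((0.25 − 1.2816 × 0.1369)/0.1323) = Φ(0.563) = 0.713.

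The figure reproduces. The number of consolidation cycles is not an input, and the endpoint it serves is measured after cycle 1 (Section 10.1.1), which both texts include.

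**The two rules side by side**

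| | Section 7.1.2 | Calendar footnote a |
|---|---|---|
| What age changes | dose, cut at 60 | number of cycles, cut at 65 |
| Cycles below 65 | up to 4 | 3–4 |
| Cycles at 65 and over | up to 4 | 1–2 |

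**Where they disagree**
- Age 65 and over, one or two cycles: consistent with both.
- Age 65 and over, third or fourth cycle: permitted by 7.1.2, outside the calendar.
- Below 65, three or four cycles: consistent with both.
- Below 65, stopping after one or two while still in remission: within the 7.1.2 ceiling, short of the calendar's range. This is the weaker conflict, because the calendar only says what patients may complete.

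**Size at 65 and over, maximum against maximum**
- Difference in cycles: 4 − 2 = 2.
- Doses, at 6 per cycle: 4 × 6 − 2 × 6 = 24 − 12 = 12.
- Time at 28 days per cycle: 112 − 56 = 56 days (8 weeks).
- Time at 42 days per cycle: 168 − 84 = 84 days (12 weeks).

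The regimen table in Section 7.1.2 gives the cycle as 28 days with a 7-day window instead. At its limits two cycles are 2 × 21 = 42 to 2 × 35 = 70 days, which does not alter the conclusion.

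**Biomarker time point.** Under the calendar no patient aged 65 or over reaches cycle 4, so the cycle 4 measurement planned in Section 10.4.2.8 could not exist for that stratum. Under Section 7.1.2 it could.

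**The case against.** The best defence is that the texts are compatible. Section 7.1.2 states only a maximum, and the calendar refines it by age within the same four-cycle frame. A site that gives an older patient one or two cycles satisfies both. This stands as far as it goes and narrows the conflict to the cases listed above. It does not remove it: Section 7.1.2 makes continuation depend on remission alone and contains an age rule of its own that says nothing about cycle number, so its reader has no signal that a lower limit applies from 65.

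Second, the end-of-consolidation endpoint is tied to the last cycle given, so it is defined for any number of cycles. That is correct; its timing changes, not its definition. Variation in cycle number is also already built in, since patients going to transplant may forgo remaining consolidation (Section 7.1.3).

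Third, the biomarker analysis is exploratory and its list of time points is qualified as applying where applicable, which can cover patients who never reach cycle 4. That makes it a point to check, not a separate contradiction.

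A reader might infer that the conflict confounds RFS and OS. The documents do not support this. Randomization is stratified at exactly 65, the two arms have the same cycle text, and cycle number is settled after randomization. None of the time origins stated for RFS or OS (Sections 1.2.4, 1.2.5, 10.4.1.1 and 13.3) depends on it. Because the trial is open label, cycle number could still drift apart by arm, but nothing in the documents shows that it does.

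**Conclusion.** Wrong as written: two current rules conflict for patients aged 65 or over at the third and fourth consolidation cycles and, more weakly, for patients below 65 who stop before three. The like-for-like gap is 2 cycles, 56–84 days (8–12 weeks) and 12 doses, taking the cycle length from the text of Section 7.1.2 and assuming each rule is used to its maximum. A reader might infer a gap of three cycles, up to 3 × 42 = 126 days, by setting four cycles against the calendar's minimum of one. Stopping at one cycle is allowed under both texts, so that third cycle is ordinary discretion and not part of the conflict.

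The consequence is heterogeneity in treatment and timing between sites, possibly between arms, and uncertainty over deviation status. It reaches a secondary endpoint, the specimens collected with it, the start of maintenance and cumulative exposure. The primary endpoint, sample size and power are untouched. The documents do not give the proportion of patients aged 65 or over, so how many are affected cannot be calculated.

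**What to change.** Reconcile Section 7.1.2 with calendar footnote a so that one cycle-number rule, including any dependence on age, appears in both places and applies to both arms. Then check the cycle 4 biomarker time point in Section 10.4.2.8, Part 2, against that rule. Which rule is right is for the sponsor to decide; none is proposed here.

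The cost is a wording change in the treatment plan or the calendar and possibly one line of the biomarker plan, with no effect on the primary analysis or sample size. In the trial report, a table of consolidation cycles given by arm and age stratum would show whether delivery differed.

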7.1.3 Maintenance therapy phase

Following count recovery from the last cycle of consolidation therapy, a bone marrow biopsy will be performed to assess for response and MRD. Patients, who remain in CR/CRi will continue on maintenance therapy while patients who do not remain in CR/CRi will be taken off study. Patients in CR/CRi will proceed with single-agent Pembrolizumab (MK-3475) (intervention arm) vs. no maintenance therapy (control arm) Q3W dosing schedule for up to 2 years, calculated from first day of maintenance therapy, according to their original randomization (*i.e.*, there will be no second randomization). For patients randomized to Arm B, Pembrolizumab (MK-3475) will be administered on Day 1 (+/- 3 days) of each maintenance cycle (each maintenance cycle is 21 days). Bone marrow samples will be obtained every 3 months while

patients are receiving maintenance or in observation to assess for MRD. Patients, who are deemed to require HSCT, can forgo any remaining protocol-defined consolidation or maintenance therapy and proceed with HSCT. Patients proceeding with HSCT will be followed for survival and SAEs through the first 100 days post-HSCT including assessment for occurrence of acute and chronic GVHD.

Maintenance Therapy Regimen Description					
Agent	Premedications ; Precautions	Dose	Route	Schedule	Cycle Length
pembrolizumab (MK-3475) (For Intervention Arm only)	Premedication with antipyretic and antihistamine may be considered. No premedication	200 mg See Section 8.1 for instructions on the preparation of the infusion	IV over 30 minutes (between 25-40 minutes) using an	Day 1(+/- 3 days) of each 21-day maintenance cycle	21 Days

Maintenance Therapy Regimen Description					
Agent	Premedications ; Precautions	Dose	Route	Schedule	Cycle Length
	with steroids	solution.	infusion set containing a low-protein binding 0.2 to 5 µm in-line filter. See Section 8.1 for compatible infusion set materials including in-line filter.		

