- h Albumin, alkaline phosphatase, total bilirubin, bicarbonate, BUN, calcium, chloride, creatinine, glucose, LDH, phosphorus, potassium, total protein, SGOT [AST], SGPT [ALT], sodium.

NCI Protocol #: 10300

Version Date: April 10, 2025

- i CBCs (with differential and platelet count), which includes WBC, ANC, platelets, Hgb, and Hct required for protocol therapy must be done <24 hours prior to the treatment cycle.
- j For women of childbearing potential, a serum or urine pregnancy test must be conducted within 72 hours prior to first dose of study treatment on both Arm A and Arm B. If the urine test is positive or cannot be confirmed as negative, a serum pregnancy test will be required.
- k TSH should be performed at baseline and <72 hours prior to each dose of Pembrolizumab (MK-3475). Additional T3 and T4 tests should be performed as clinically indicated, if TSH is abnormal, if symptoms are suggestive of thyroid dysfunction.
- l Bone marrow aspirate is required to be submitted for central MRD testing as outline in Section 5. Submit to [name] lab at Children's Hospital Los Angeles. Results will be forwarded to the submitting institution within 1-2 business days of receipt of the bone marrow aspirate samples. Local bone marrow biopsy (aspirate) must be performed at the indicated time points and should follow the institutional standard of care.
- m To be collected between Day 14 and Day 21.
- n To be collected between Day 28 and Day 42.
- o To be collected at the end of consolidation therapy only.
- p Bone marrow aspirations every 3 months during maintenance/observation phase are optional and should only be collected when part of standard of care.
- q To be collected every 3 months during maintenance phase.
- r Blood collection for the immune cell subset analysis and Olink assay only.
- s Bone marrow aspiration and blood should be collected for MRD status in patients who have not relapse. For patients who have relapsed, bone marrow core biopsies, bone marrow aspirate, and blood should be collected. Blood collection for cfDNA will be obtained at the same time-points as blood collection for MRD status.
- t Repeat TTE should be performed before 5+2 reinduction.
- u PT, PTT, and fibrinogen will be additionally collected on days 8 and 9 (pre- and post-) in the pembrolizumab arm.

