- v CBC and CMP will be obtained within 3 days of receipt of each pembrolizumab dose in the pembrolizumab arm and every 3 weeks during treatment and every 6 (+/- 1 week) weeks during observation for patients in the control arm.
- w ECGs performed after screening will be done as medically indicated.
- x CT chest should be considered as a part of screening (optional)
- y Screening period is up to 21 days
- z At time of Post-Consolidation Cycle 1 bone marrow collection (+/- 3 days)
- α Refer to Section 5.1 Summary Table for Specimen Collection and Appendix F Skin Punch Biopsy Verification Form
- β (+/- 3) days
- £ Observation visits in Maintenance on control arm may be extended to 6 weeks (+/- 1 week).

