- >50% increase in marrow blasts over baseline (a minimum 15% point increase is required in cases with <30% blasts at baseline; or persistent marrow blast percentage of >70% over at least 3 mo; without at least a 100% improvement in ANC to an absolute level ($>0.5 \times 10^9/L$ [$500/\mu L$], and/or platelet count to $>50 \times 10^9/L$ [$50\,000/\mu L$] nontransfused)
- >50% increase in peripheral blasts (WBC \times % blasts) to $>25 \times 10^9/L$ ($>25\,000/\mu L$) (in the absence of differentiation syndrome)
- New extramedullary disease Some protocols may allow transient addition of hydroxyurea to lower blast counts

“Progressive disease” is usually accompanied by a decline in ANC and platelets and increased transfusion requirement and decline in performance status or increase in symptoms

Relapse

Hematologic relapse (after CRMRD⁻, CR, CRi) Bone marrow blasts $\geq 5\%$; or reappearance of blasts in the blood; or development of extramedullary disease

Molecular relapse (after CRMRD⁻) If studied pretreatment, reoccurrence of MRD as assessed by RT-qPCR or by MFC

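### After consolidation, the blood counts that can reveal relapse run on different schedules in the two arms, and no analysis rule handles this for RFS and DOR (or for EFS through late relapse)

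*Combined protocol and SAP*

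**What the plan says.** - **Pembrolizumab arm, blood counts.** Study Calendar (Section 12), footnote v: "CBC and CMP will be obtained within 3 days of receipt of each pembrolizumab dose". Footnote f and Section 7.1.3 set 21-day maintenance cycles for up to 2 years.
- **Control arm, blood counts and visits.** Footnote v sets counts "every 3 weeks during treatment and every 6 (+/- 1 week) weeks during observation for patients in the control arm". Footnote £ allows the visits to follow: "Observation visits in Maintenance on control arm may be extended to 6 weeks (+/- 1 week".
- **End of phase.** Footnote b, attached to the End of Maintenance / Observation column: "End of treatment visit will be immediately following final dose of Pembrolizumab (MK-3475". No trigger is given for controls.
- **Afterwards.** Footnote c: "After completing study treatment, clinical follow-up assessments are required every 6 months from date of therapy discontinuation". It mentions 3-monthly institutional practice as not required, and continues central MRD testing, without an interval, for patients who reached undetectable MRD.
- **Marrow.** Section 7.1.3: "Bone marrow samples will be obtained every 3 months while" patients are on maintenance or observation. Footnote p: "Bone marrow aspirations every 3 months during maintenance/observation phase are optional and should only be collected when part of standard of care".
- **Shared sampling.** The Section 5.1 specimen table makes 3-monthly MRD and Streck blood mandatory in maintenance/observation, with no distinction by arm.
- **Relapse.** Appendix D counts marrow blasts of at least 5%, or "reappearance of blasts in the blood; or development of extramedullary disease".
- **Analysis.** Section 10.1 gives Kaplan-Meier medians with 95% confidence intervals for RFS and DOR, and censors DOR at the last evaluable disease assessment. Sections 10.1, 10.4.1.1 and 13.3 contain no relapse-dating rule, interval-censored analysis or sensitivity analysis for unequal visits.

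**The concern.** A relapse is dated when someone looks. Because blood blasts alone suffice, a blood-count schedule is also a relapse-detection schedule, and here it depends on the arm in two opposite ways.

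While pembrolizumab is being given, that arm is looked at about twice as often as control, so its relapses are dated slightly earlier. Once a patient permanently stops pembrolizumab in maintenance, the end visit falls due at once and required results become 6-monthly, so relapses in that patient may be dated later than in a control still under observation. Sections 7.1.1 and 7.1.2 keep such a patient on study chemotherapy in induction and consolidation; Section 7.1.3 has no counterpart for maintenance. Section 7.3 continues assessments when dosing is interrupted and does not mention permanent stopping.

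RFS, DOR and EFS are the secondary endpoints that would show whether a deeper response lasts. The net bias depends on how many patients stop pembrolizumab, so a reader of the results could not correct for it.

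**Working it through.** **Plan's own figure.** The only design calculation bearing on a comparison between arms is the power for the primary endpoint: 75% versus 50%, 25 per arm, one-sided 0.10.

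- Pooled SE = √(2 × 0.625 × 0.375 / 25) = 0.1369
- Unpooled SE = √((0.25 + 0.1875) / 25) = 0.1323
- Power = Φ((0.25 − 1.2816 × 0.1369) / 0.1323) = Φ(0.563) = 0.713

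This reproduces the stated 71%. The plan gives no event count, hazard ratio or power for RFS, DOR or EFS.

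**Mean detection delay.** If relapse falls at random between visits and is found at the next one, mean delay = interval / 2.

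| Situation | Interval (weeks) | Mean delay (weeks) |
|---|---|---|
| Pembrolizumab, on dosing | 3 | 1.5 |
| Control, observation | 6 (7 with the window) | 3 (3.5) |
| Stopped early, 3-monthly practice | 13 | 6.5 |
| Stopped early, required minimum | 26 | 13 |

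On schedule, 3 − 1.5 = 1.5 weeks, against pembrolizumab. After early stopping, 6.5 − 3 = 3.5 weeks to 13 − 3 = 10 weeks, in favour of pembrolizumab, per affected relapse.

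**Effect on the hazard ratio when there is no true effect.** Simulation with 100,000 patients per arm and a Cox model with Efron ties. Assumptions not in the documents: exponential time to relapse; relapse found only at scheduled visits; 6-monthly visits after early stopping, and in both arms after 2 years; 3 years of follow-up; median time to relapse and proportion stopping early varied as shown. Entries are pembrolizumab versus control.

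| Stop early within 2 years | Median 6 months | 12 months | 24 months |
|---|---|---|---|
| 0% | 1.04 | 1.02 | 1.01 |
| 20% | 1.01 | 1.00 | 0.99 |
| 40% | 0.99 | 0.98 | 0.98 |
| 80% | 0.94 | 0.95 | 0.96 |

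Mean delay for relapses within 2 years was about 3.1 weeks in control. In the pembrolizumab arm it was 1.5 weeks with no early stopping, 3.2 to 3.9 weeks at 40%, and 5.7 to 7.2 weeks at 80%.

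**At trial size.** With an assumed 18 remitters per arm and a nominal one-sided 10% test (the plan names none), false positives favouring pembrolizumab ran from about 9% with no early stopping to 12–16% at 80%. Simulation error is about 1 point.

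**The case against.** The strongest reply is that both arms share a 3-monthly disease-sampling schedule with mandatory blood, so the disease is looked at equally where it matters. The sampling is real and limits the problem. However, those tubes go to central research laboratories, and the plan does not make them a hematologic relapse assessment. Coverage of controls is also worded unevenly: Section 5.1 says maintenance therapy/observation, while footnote q says maintenance phase. The conflict over marrow applies to both arms alike, but if marrow is optional, the treating team in an open-label trial decides when to look.

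A reader might infer that relapse in patients who stop pembrolizumab is typically dated 10 weeks late relative to control. The documents do not support that. The 13-week delay assumes the required minimum and nothing found in between. Footnote c mentions 3-monthly practice, Section 7.4 says at least 6-monthly and follows unacceptable adverse events to resolution or stabilization, and symptomatic relapses present between visits. A reader might also take it as stated that controls stay on 6-weekly visits while a matched pembrolizumab patient leaves. Footnote £ is permissive (footnote v, on blood counts, is not), footnote c is worded for all patients, and its start for controls is undefined. The asymmetry is an inference from the pembrolizumab-based trigger, though no text prevents it.

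Precision is a fair point too. With 24 relapses or deaths split evenly (an illustration), SE of log HR = √(4/24) = 0.41, and a 95% interval spans a factor of exp(1.96 × 0.41) ≈ 2.2 either way. A shift of 1 to 4% would be invisible. That argues for a cheap remedy, not for leaving the schedule dependent on arm.

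**Conclusion.** The concern holds in a limited form. Visit and blood-count ascertainment of relapse differs by arm in maintenance/observation, can differ further after permanent discontinuation of pembrolizumab, and is not handled in the analysis.

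It bears on RFS and DOR. It would be too strong to say that EFS as a whole is compromised: induction failure is assessed on the same rules in both arms and death does not depend on visits, so EFS is touched only through post-consolidation relapse. The primary endpoint, assessed after the first consolidation cycle on common rules, and OS are unaffected. The plan names Kaplan-Meier estimation for RFS and DOR and no between-arm test.

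Under the simulation assumptions the apparent hazard ratio stays within about 0.98 to 1.04 when up to 40% stop early, and reaches 0.94 to 0.96 only at 80%. Relapses found between visits would shrink these shifts. The point merits a change because the direction is unpredictable and the remedy is cheap, not because the likely bias is large.

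**What to change.** 1. **One clock.** In the Study Calendar, define the maintenance/observation relapse assessment (visit plus CBC with differential) and the end-of-phase visit from the post-consolidation marrow in both arms. Use one common interval, for example the 6 weeks already used for control counts, until relapse, HSCT or 2 years, whether or not pembrolizumab is still given. Rewrite footnotes b, c, v and £ to match.
2. **Dating rule.** Calling the 3-weekly pre-dose counts safety tests would not equalise detection, because blasts seen there still define relapse. Add a sensitivity analysis for RFS, DOR and EFS that moves each relapse to the next common scheduled assessment, or an interval-censored analysis.
3. **Marrow.** Reconcile Section 7.1.3 with footnote p on the 3-monthly marrow.

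Cost: calendar wording, some blood counts for patients who stop pembrolizumab early, and one extra analysis. A 6-week grid adds no control visits beyond the blood-count schedule in footnote v, and treatment is unchanged.
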